Also, long COVID can be regarded as a condition of chronic stress, which could theoretically be associated with disturbances of the hypothalamo-pituitary-adrenal (HPA) axis, although no studies on HPA axis (dys)function in long COVID have been reported yet.

The aims of this study are to describe the standardized evaluation of the psychopathological and neurocognitive function of long COVID patients and their evolution over time; to explore the cross-sectional and longitudinal association

between long COVID symptoms and immunological measures; and to examine the neuro-endocrine (HPA-axis) characteristics of long COVID syndrome.

Three participant groups will be included: 1) long COVID patients with neuropsychological complaints (P), 2) COVID-survivors without persistent complaints (Ca) and 3) healthy volunteers (Cb).

This is a longitudinal study, starting from November 1st 2021. Enrollment will continue for an estimated period of 24 months, depending on the time course of the epidemic curve. Last-patient-in is expected no later than November 1st, 2023. The study will be organized into three work packages (WP1, WP2 and WP3). WP1 includes psychiatric assessments using questionnaires and blood sampling and is the standard WP for every participant. WP2 includes cortisol measurement using saliva sampling for patients and controls from Cb. who do not fulfill specific exclusion criteria (pregnancy, breastfeeding, hormonal therapy with exception of contraceptives, cortisol treatment). Finally, WP3 includes an extensive neurocognitive assessment by a specialized neuropsychologist for both patients and controls from Ca who do not fulfill specific exclusion criteria (sedative medication, pre-existing neurological disease, severe substance abuse, and IQ < 90).

Patients and controls from Ca will be referred mainly by the University Hospital of Antwerp (UZA) and by long COVID patient support groups and enrolled at first visit to UPCD, where follow-up will also take place at 3, 6 and 12 months. WP1 will be performed at each timepoint, while WP2 and WP3 will only be carried out at baseline and 6 months.

Total sample size is estimated on 130 participants.

List of Abbreviations

- ACTH: adrenocorticotrophic hormone
- BACS: brief assessment of cognition in schizophrenia
- BDI: Beck depression index
- Ca: Control group a: COVID-survivors without NP complaints
- CAR: cortisol awakening response
- Cb: Control group b: healthy controls
- CFS: chronic fatigue syndrome

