1.4. Insomnia

Genome Wide Association Studies have demonstrated a strong correlation of the genetic risk of insomnia with depression and anxiety (36,37). Furthermore, insomnia has been identified as a primary risk factor for the onset, persistence and relapse of anxiety, depression and PTSD. In a Network Outcome Analysis of 768 individuals without history of depression, *difficulty initiating sleep* was one of only five direct predictors of first-onset major depressive disorder after six years follow-up (38).

Depending on the study methods, in long COVID patients the prevalence of clinically relevant insomnia was estimated between 5% (diagnosis of insomnia disorder in electronic medical records <6m following infection) and 24% (self-rated insomnia symptoms above clinical cut-off at 3-month follow-up). These symptoms could represent an important risk factor in the subsequent development of anxiety and depressive disorders, and a key mechanism underlying cognitive deficits.

2. Research Objectives

- 1) Describe the standardized evaluation of the psychopathological and neurocognitive function of long COVID NP patients and their evolution over time;
- 2) Explore the cross-sectional and longitudinal association between long COVID NP symptoms and immunological measures;
- 3) Define the prevalence and clinical characteristics of insomnia in long COVID NP patients, as well as its correlation to the clinical psychiatric and neurocognitive symptom domains;
- 4) Compare the immunological profile of long COVID NP patients to those of existing cohorts of comparable primary psychiatric conditions and healthy controls;
- 5) To examine the neuro-endocrine (HPA-axis) characteristics of long COVID syndrome

3. Methodology

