The Rey Auditory-Verbal Learning Test (RAVLT) (54,55) is administered to evaluate auditory-verbal memory for unrelated information. The variables we use for the analysis are total immediate recall (over 5 trials) (the maximum learning score is 75), long-term delayed recall (after a 20-min time interval; the

maximum recall score is 15) and long-term delayed recognition (after a 20-min time interval; the maximum recognition score is 15).

Visuospatial memory for related information is assessed by means of the Complex Figure Test (Rey figure) (CFT-R) (54–56). The two measures we use are immediate recall and long-term delayed recall (after a 20-min time interval) of recently learned information.

- *Visuospatial functions*

The copy of the Complex Figure Test (Rey figure) (RCFT-R) (54–56) is administered to evaluate visuospatial judgement. The total score (with a maximum of 36) is recorded.

- *Language*

In our study we administer the short form of the Boston Naming Test (BNT-SF) (66) to measure word finding (i.e., naming of 29 objects). The outcome measure is the total correct answers (with a maximum of 29).

- *Executive functions*

The Controlled Oral Word Association Test (57) and the Word Fluency Test (WFT) (67) are used to assess phonetic verbal fluency and semantic verbal fluency, respectively. The total words generated is used as outcome measure for both tests.

The Subtests Similarities and Matrix Reasoning from the Wechsler Adult Intelligence Scale (4th Edition) (WAIS-IV (S) and WAIS-IV (MR)) (58) are selected to measure verbal abstract reasoning and non-verbal abstract reasoning, respectively. The total raw score is used as outcome measure for both subtests.

The Tower of London Test (59) is used to evaluate planning and problem solving. The outcome variables are the total correct score, the total move score and the total problem-solving time.

- *Psychomotor speed/coordination*

The conditions 4 and 5 of the Trail Making Test from the Delis-Kaplan Executive Function System (D-KEFS (TMT)) (68) are administered to evaluate psychomotor speed with a cognitive component (cognitive flexibility) (condition 4) and psychomotor speed without a cognitive component (condition 5). For both conditions, the total raw score (total time) is used as outcome measure.

The Purdue Pegboard Test (60) is used to assess psychomotor coordination. The total raw score (or the average of three trials, each trial with a time limit of 30 s) for the preferred hand, for the

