non-preferred hand and for both hands are used as outcome measures.

- *Cognitive functioning in daily life*

The Cognitive Failure Questionnaire (CFQ) (69) is used to detect possible cognitive problems (or failures) which are noticed by patients during daily life activities in the past four weeks. This self-report scale consists of 25 items with a rating of 0 (never), 1 (rarely), 2 (sometimes), 3 (often) or 4 (very often) for each item. The total score (with a maximum of 100) is used as outcome measure.

- *Fatigue*

The Fatigue Severity Scale (FSS) (61) is used to detect possible complaints of fatigue in daily life by the patient. This self-report scale consists of 9 items about fatigue, its severity and how it can affect several daily activities. The items are scored on a 7-point rating scale from 1 (strongly disagree) to 7 (strongly agree). The total score is used as outcome measure (with a maximum of 63).

- Cognitive rehabilitation

The COVID-19 patients are divided into two groups: a treatment group and a non-treatment group. The patients in the treatment group follow a cognitive rehabilitation program. This program consists of 12 group sessions of one hour (one session per week). A maximum of 6 patients participate to a group session. Each session consists of two cognitive rehabilitation methods. These are restorative therapy (which means administering several cognitive exercises (with increased level of complexity) in order to improve the specific cognitive deficits of each individual patient (as was detected by means of the neuropsychological baseline evaluation) with regard to attention, memory and/or executive functions) and (2) compensatory therapy (which means teaching compensation strategies in order to cope better with the cognitive disabilities concerning attention, memory and/or executive functions that each individual patient experiences during daily life activities). The patients in the non-treatment group receive no cognitive rehabilitation program.

- Neuropsychological reassessment

The patients in both groups (treatment group versus non-treatment group) undergo a neuropsychological reassessment after approximately 3 months. For some tests (RAVLT, CFT-T (Taylor figure), COWAT and WFT) a parallel

version is used to minimize a possible practice effect. Of course, for the treatment group this neuropsychological reassessment is necessary to evaluate the progression of cognitive functioning after 3 months of cognitive rehabilitation.

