3.3.6. Follow-up measures

Depending on the clinical findings, treatment with psychopharmacological compounds may be initiated or patients may be enrolled in a group cognitive remediation program contingent upon clinical indication. Follow-up visits with psychiatric evaluation, self-rating scales and blood sampling will take place every 3

months for a maximum of one year. Follow-up neuropsychological assessment will take place once after 6 months.

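### Parallel test versions appear only at reassessment, with no counterbalancing or version term, so patients' mean change on these tests includes any difference between versions

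*Combined protocol and SAP*

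**What the plan says.** In section 3.3.2 the battery uses the Rey figure for visual memory: "Visuospatial memory for related information is assessed by means of the Complex Figure Test (Rey figure) (CFT-R". It also uses it for visuospatial judgement: "The copy of the Complex Figure Test (Rey figure) (RCFT-R". Table 1 lists the same figure. The paragraph on reassessment, later in 3.3.2, brings in other versions: "For some tests (RAVLT, CFT-T (Taylor figure), COWAT and WFT) a parallel" "version is used to minimize a possible practice effect". That is the only reason given.

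The documents do not mention alternating the order, equating the versions, version-specific norms or recording which version was used. The longitudinal models in section 3.5 include time, treatment group and baseline covariates, but no test version.

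The retest schedule is stated inconsistently:

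- Section 3.3.2: patients in both the treatment and non-treatment groups "undergo a neuropsychological reassessment after approximately 3 months".
- Section 3.3.6: "Follow-up neuropsychological assessment will take place once after 6 months".
- Synopsis, which assigns WP3 to patients and Ca: "while WP2 and WP3 will only be carried out at baseline and 6 months".
- Figure 5: two neurocognitive assessments for patients and one, at baseline, for Ca.

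The first objective in section 2 is to "Describe the standardized evaluation of the psychopathological and neurocognitive function of long COVID NP patients and their evolution over time". Section 3.4 lists cognition at baseline and follow-up as an endpoint for the subgroup.

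**The concern.** Parallel versions are a sensible way to reduce practice effects. If everyone takes one version first and the other second, however, a difference in difficulty between versions cannot be told apart from a change in the patient. A harder second version looks like decline and an easier one looks like recovery. Adding a version term at analysis would not help, because in patients it would be collinear with time.

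The outcomes exposed are raw totals: three RAVLT scores, two figure recall scores, the figure copy score (if the copy is also made from the Taylor figure), and total words on the COWAT and WFT. What is at stake is the description of how patients' cognition evolves under objective 1, and the progression within the treated group that 3.3.2 says reassessment is meant to evaluate.

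**Working it through.** The plan gives no version difference, no SD of change and no retest correlation, so there is no figure of its own to reproduce. The check has two parts.

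**Identifiability.** With a fixed order, for one patient:

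E(follow-up − baseline) = true change + residual practice + (version B − version A).

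The last term is the same for every patient and occurs only at follow-up, so it is absorbed by time. Its effect on each quantity of interest is:

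- Mean change in patients, or in the treated group alone: biased one for one.
- Treated minus non-treated change, same order in both: a common shift cancels.
- Association of a baseline predictor with follow-up score: a common shift moves the intercept or the time effect, not the slope on the predictor.
- Patient change minus Ca change: a common shift cancels, but only if Ca is retested with the same versions in the same order.

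**Size, as an illustration.** From the documents: 50 patients (section 3.1). This is an upper bound for those retested, because WP3 has its own exclusions. Assumed: n=25 as a smaller subgroup, retest correlation r of 0.5 or 0.7, a version difference d of 0.1 to 0.3 baseline SD, no true change or residual practice, and a two-sided paired t-test of mean change at 0.05.

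- SD of change = √(2(1−r)): 1.00 at r=0.5 and 0.775 at r=0.7.
- SE of mean change = √(2(1−r)/n): at n=50, r=0.7, √(0.6/50) = 0.110 SD.
- Noncentrality = d√n / √(2(1−r)): at d=0.2, n=50, r=0.7, 0.2 × 7.071 / 0.775 = 1.83.
- False-positive rate = P(|T| > t(0.975, n−1)), with T noncentral t on n−1 df.

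| n | r | d=0.1 | d=0.2 | d=0.3 |
|---|---|---|---|---|
| 25 | 0.5 | 8% | 16% | 30% |
| 25 | 0.7 | 10% | 24% | 46% |
| 50 | 0.5 | 11% | 28% | 55% |
| 50 | 0.7 | 15% | 43% | 77% |

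**Effect of alternating the order.** With half of n=50 in each order and the order in the model, mean change is the average of the two sequence means. Its SE is √(0.6/4 × (1/25 + 1/25)) = √0.012 = 0.110 SD, the same as before. In 20,000 simulated studies at r=0.7 and d from 0.1 to 0.5, the mean estimate was within 0.001 of zero and the false-positive rate was 4.9% to 5.2%. Without the version term, alternating alone removed the bias but made the test conservative (3.6% at d=0.3, 2.0% at d=0.5). In the same simulations under fixed order, a comparison of 25 with 25 patients kept its error rate at 4.9% to 5.1%, which confirms that the shift cancels there.

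**The case against.** Several stronger readings are tempting, and the documents do not support them.

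- **That a fixed order is documented for all four tests.** It is explicit only for the complex figure. For the RAVLT, COWAT and WFT it is inferred, because a parallel version is mentioned only at reassessment and nothing says the order varies. The inference is natural, but it is an inference.
- **That no analysis could separate version from change.** This is true of patients' own change. A Ca group retested on the same versions would remove a common shift from patient-minus-Ca change. The synopsis implies such a retest, while Figure 5 and the reassessment text do not show one.
- **That the planned models are biased.** Section 3.5 concentrates on associations with inflammation and insomnia and adjusts for treatment group. A common additive shift does not reach those estimates. It would do so only if the version effect differed by group or ability level.
- **That the rates above forecast this study's error.** They rest on assumed shifts and correlations and on a test of mean change that 3.5 does not specify. Nothing in the documents shows that the versions differ at all.
- **That the protocol expects worsening, so a harder second version would confirm its hypothesis.** Section 1.2 reports another group's unpublished preliminary finding. No objective or hypothesis here predicts decline.

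It can also be said that neurocognitive evaluation is part of routine care, that patients receive a report, and that baseline findings guide rehabilitation. Changing the baseline version for half the patients is therefore more than an administrative edit. That stands as a cost. It does not remove the confounding, because objective 1 and the follow-up cognition endpoint depend on change over time, and for these tests the plan does not secure any means of separating that change from version.

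**Conclusion.** The concern holds with a limited scope. For the complex figure, and on the natural reading for the RAVLT, COWAT and WFT, mean within-patient change cannot be separated from a difference between versions. This affects the description of cognitive evolution in patients and progression within the treated group. It does not affect treated versus non-treated contrasts or baseline-predictor associations under a common additive shift, nor tests given in the same version twice, which keep their practice effect.

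The size is unknown. Under the stated assumptions, version differences of 0.1 to 0.3 SD would be called a change in about 8% to 46% of studies at n=25 and 11% to 77% at n=50, rather than 5%. Because the within-patient comparison is precise, even a modest difference between versions would matter. The change is worth making because it is cheap.

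**What to change.** - In 3.3.2, for participants not yet tested, alternate the version order within P and within Ca, so that half start with the Rey figure and the current first versions and half with the Taylor figure and the parallel versions. Record the version at every session.
- In 3.5, include test version as a fixed effect for these four tests, including in the baseline comparison of P with Ca.
- For participants already tested in fixed order, report mean change on these tests as not separable from version, or report it relative to Ca if Ca is retested in the same order.
- Reconcile the synopsis with Figure 5 on whether Ca is retested, and the 3-month with the 6-month reassessment time.

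The cost is mixed versions at baseline, one degree of freedom per model, and clinical reports that must state which version was used. Alternating needs no extra visits, tests or participants, and under the illustration the standard error of mean change stays at 0.110 SD.

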3.3.3. Blood sampling

Blood samples will be collected in a standardized manner by venipuncture. Two blood vials will be collected and processed to perform the following analyses:

- serum collection tube(s) allowing for HERV-W ENV and serological assays
- plasma collection tubes for the assessment of other immune-related biomarkers (including but not limited to CRP, IL-6, IL-1b, TNF-a, IFN-g, tryptophan, kynurene, 3-OH-kynurene, quinolinic acid, kynurenic acid, enzymes of the kynurene pathway).

A maximum of 35ml blood will be collected during each visit, clinical test sampling included. Study-dedicated blood tubes will be processed for respective plasma and serum extraction according to standardized protocols and plasma / serum will subsequently be stored at -80°C until analysis or elimination.

Residual pellet material of whole blood centrifugation for plasma collection will be utilized for DNA extraction to perform additional genotyping. Emerging evidence has linked specific DNA haplotypes with increased risk of psychiatric morbidity. Exploration of specific immune related genes in post-COVID NP patients might reveal insights in genetic predisposition for infection-driven psychiatric decompensation. DNA sequencing of immune related loci (including but not limited to MHC-II) will be performed on residual pellet material from centrifugated blood collection tubes for plasma procurement if specific additional consent is obtained from the participant. If such consent is not granted, residual pellet material will be discarded after plasma collection.

3.3.4. Cortisol measurements (HPA axis)

Salivary cortisol measures will be used as functional measure of the HPA axis activity, as the unbound cortisol fraction in saliva is highly correlated to plasma cortisol (62–64). Baseline diurnal cortisol and CAR levels will be measured using saliva, collected at home with Salivette® (Sarstedt) synthetic swabs. The rationale behind the choice of home sampling, is to maximize normal circumstances and to minimize stress related to the measuring procedure. Participants are also asked to perform the sampling on two consecutive days with no anticipated excessive stress or physical or mental efforts. The Salivette® sampling method is easy and minimally invasive. Participants put the swabs in their mouth and move them around for

approximately 60 seconds. Participants are required to refrain from smoking, drinking and eating or brushing the teeth 30 minutes before each measurement. The sampling times are immediately upon awakening, 30, 45 and 60 minutes after awakening (CAR). All samples will be analyzed through electrochemiluminescence immunoassay at the laboratory of the Antwerp University Hospital. The lower detection limit of cortisol is 0.544 ng/ml. This value is assigned whenever cortisol levels were below the detection threshold.

3.3.5. Electronic clinical records

The following demographic and clinical variables will be collected through electronic clinical records. If certain data is unavailable from the records, the participant may be contacted by a member of the research team for an additional interview.

- Demographics: age, gender
- Clinical diagnosis at baseline psychiatric evaluation
- Medical history
- Psychiatric history
- Family psychiatric history
- Current + past medication use
- Metabolic parameters: weight, length, waist circumference, triglycerides (TG), HDL-cholesterol, blood pressure, fasting plasma glucose
- Current substance abuse: nicotine, alcohol, cannabis
- If available, results of RT-PCR of SARS-CoV-2 on a nasopharyngeal swab or of SARS-CoV-2 serology
- Date of acute infection, duration of NP symptoms of long Covid
- If available, brain imaging, polysomnography or other technical exams performed during or after COVID-19 infection, including lab results during acute COVID-19 infection
- If available: inflammatory parameters in lab result during acute infection. Otherwise: inflammatory parameters of last clinical lab result (including but not limited to white blood cell count)
- SARS-CoV-2 vaccination status

3.3.6. Follow-up measures

Depending on the clinical findings, treatment with psychopharmacological compounds may be initiated or patients may be enrolled in a group cognitive remediation program contingent upon clinical indication. Follow-up visits with psychiatric evaluation, self-rating scales and blood sampling will take place every 3

months for a maximum of one year. Follow-up neuropsychological assessment will take place once after 6 months.

3.4. Endpoint measurements

“NP symptoms”

- Baseline and follow-up scores on clinical scales of depression, anxiety, and insomnia
- (subgroup) Baseline and follow-up cognitive functioning

“Inflammation”

- Quantitative measurement of HERV-W-ENV in serum at baseline
- Calculation of systemic immune inflammatory index (SII= thrombocyte count x neutrophile count / lymphocyte count) at baseline and follow-up
- Quantitative analysis of CRP and IL-6 at baseline and follow-up
- Quantitative analysis of kynurenine metabolites at baseline and follow-up

(subgroup) *“HPA axis”*

- CAR

3.5. Statistical analysis

CAPRI has ongoing collaborations with StatUA and BIOMINA for statistical analyses of past and ongoing projects involving biomarker-data. In this project, we will study cross-sectional and bidirectional longitudinal associations between *NP symptoms* and *Inflammation* or *Insomnia* (cfr above).

To study the cross-sectional association using all available data, we will stack data from all timepoints in one cross-sectional dataset. To account for the fact that one person can have multiple observations in this combined cross-sectional dataset, we will analyze the association between NP symptoms and inflammation / insomnia (measured at the same timepoint) using linear mixed models with timepoint as repeated effect and patient identifier as within-subject effect and using an unstructured correlation matrix. Estimates from this model thus represent the cross-sectional association between predictor and outcome.

For longitudinal analyses the effect of baseline *Inflammation* and *Insomnia* on *NP symptoms* at 3- and 6-month follow-up will be evaluated using linear mixed models with time as repeated effect and patient identifier as within-subject effect and using an unstructured correlation matrix. Baseline predictor by time interaction (time coded as 0, 3, or 6) will be included to test differences in slope but retained only in models when statistically significant. Treatment group (antidepressant treatment, insomnia treatment, cognitive remediation, a combination, or none) will be included

as predictor. Baseline values of NP symptoms will be included as covariates, and all other covariates measured at baseline as well.

